## 5. Analysis Populations

- For all analyses, subjects will be analyzed according to the dose and treatment received, not the dose and treatment to which subjects were randomized.
- Subjects who discontinued from the study before their assigned end of study day (referred to as early termination subjects) will be excluded from pharmacokinetic and pharmacodynamic parameter summary calculations.
- The PD population will include all subjects who received study drug and have at least 1 estimable PD parameter after dosing. For baseline-adjusted analyses, subjects must also have at least one valid baseline sample between screening to dose administration on day 1. Subjects without a valid baseline sample will be excluded from PD assessments where the derived metric is baseline adjusted.
- The PK population will include all subjects who received study drug and have at least 1 estimable PK parameter after dosing. Subjects with all samples below the lower limit of quantification will not be included in PK population summaries.
- The PK/PD population (exposure-response population) will be used for the model-based exposure-response analysis. This population includes all subjects from the PK and PD populations, including those who received placebo treatment, as well as subjects with PK samples below the lower limit of quantification.

- The safety population will include all subjects who received at least 1 dose of any of the study drugs,

## **6. Data Screening and Acceptance**

### **6.1. Handling of Missing and Incomplete Data**

The following imputation of missing values will be done:

- Pharmacokinetic measurements below the quantification limits will be considered equal to zero for all analyses.
- Non-pharmacokinetic measurements (e.g., neopterin, MxA) below the quantification limits will be considered equal to the lower limit of quantification for all analyses unless explicitly noted otherwise.
- Missing pharmacokinetic or pharmacodynamic data (e.g., skipped outpatient visit) will not be imputed.
- For baseline adjusted measures, samples from Day 1, time 0 will be used for calculating this derived metric. In cases where the Day 1, time 0 sample is missing or invalid, the sample collected at check-in (Day -1) will be used, followed by the screening sample. If none of these samples are available or valid, then no baseline value will be calculated for the subject.

## **7. General Statistical Considerations**

All data will be presented in data listings. Data from subjects excluded from the analysis population will be presented in the data listings, but not included in the calculation of summary statistics.

### **7.1. Subject Disposition**

The number of subjects who enroll in the study and the number and percentage of subjects who complete each assessment will be presented. The frequency and percentage of subjects who withdraw or discontinue from the study and the reason for withdrawal or discontinuation will be summarized. In addition, significant known protocol deviations will be noted for individual subjects.

### **7.2. Demographics and Baseline Characteristics**

Descriptive statistics will be used to summarize demographic and baseline subject characteristics for age, sex, weight, body mass index, race, and ethnicity. For continuous variables, the mean,

median, standard deviation (SD), minimum, and maximum values will be reported. For categorical (nominal) variables, the number and percentage of subjects (or observations) will be reported.

### **7.3. Pharmacodynamic Analysis**

#### **7.3.1 Neopterin**

Individual neopterin versus time plots will be presented for each participant. For neopterin, AUEC and maximum increase from baseline will be calculated for each participant using all on treatment timepoints. Calculations will be performed using non-compartmental analysis packages available in statistical software. The primary analysis with neopterin will use baseline-adjusted AUEC and maximum increase from baseline, while other derived measures (AUEC, pAUEC) may be calculated to evaluate how derived PD metrics impact trial design. PD parameters of IFN  $\beta$ -1a and pegIFN  $\beta$ -1a, and placebo groups will be listed and summarized using descriptive statistics (n, mean, SD, coefficient of variation, minimum, median, interquartile range, and maximum) for each treatment arm.

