## 5.9.6 Primary Analysis

### 5.9.6.1 Pharmacodynamic Analyses

#### Neopterin and MxA protein

AUEC will be calculated for each subject. For each dose, separate intervals will be used for the AUEC assessment to truncate noise introduced from baseline fluctuations. Maximum decrease from baseline will be determined from all sampled timepoints. For both assessments and biomarkers, measures will be log-transformed and utilize an ANCOVA approach for calculating geometric means and 90% confidence intervals for each treatment. PD parameters of Avonex or Plegridy will be listed and summarized using descriptive statistics (n, geometric mean, coefficient of variation, minimum, median, and maximum).

Separate population PD analyses will be conducted using nonlinear mixed effect modeling with NONMEM. AUECs calculated for each subject from all doses for a drug and placebo patient will be combined and evaluated assuming a saturating  $E_{max}$  relationship to characterize system parameters such as  $E_{max}$  and  $EC_{50}$ .

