## Change Log

Version	Section	Changes
2	5	Added that ‘Subjects who did not complete their treatment (referred to as early termination subjects) will not be included in PK and PD parameter summary calculations.’
2	7.3.1, 7.3.2	The descriptive summary for PD parameters is changed from geometric mean to mean. Changes in PD parameter from baseline for placebo and low doses may have negative values and would not allow for calculation of geometric mean. Text describing the primary, secondary, and exploratory PD parameter was updated for clarity.
2	General	Typographical changes included throughout

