## 7.5. PK/PD Analyses

The dose- and exposure-response relationship between baseline-adjusted AUEC for neopterin and  $\Delta\text{Neopterin}_{\text{dec, max}}$  and IFN  $\beta$ -1a and pegIFN  $\beta$ -1a will be explored graphically (separate assessments for both response measures). Based on these observations, model-based analyses using statistical software will be conducted separately for each drug with respect to each of the above-mentioned PD measures.

The model-based analysis will explore both dose and exposure (i.e.,  $AUC_{0-\text{inf}}$ , referred to as AUC below) as the dependent variable. Data for all dose levels for a drug, as well as placebo, will be combined for the analysis. Model selection will be based on the initial graphical assessment and will be selected from one of the following structures – linear,  $E_{\text{max}}$ , and sigmoidal. Multiple models may be evaluated based on the initial graphical analysis, in which case model selection will be based on a combination of goodness of fit plots, parameter uncertainty (i.e., parameter confidence intervals including zero), and Akaike’s information criterion (AIC). General representations for each of the model structures and parameterizations is shown below:

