### *Exposure-relationship*

Linear: Response  $\sim E_0 + \text{Slope} * \text{AUC}$

$E_{\text{max}}$ : Response  $\sim E_0 + E_{\text{max,exp}} * \text{AUC} / (\text{AUC} + \text{EC}_{50})$

Sigmoidal: Response  $\sim E_0 + E_{\text{max,exp}} * \text{AUC}^\gamma / (\text{AUC}^\gamma + \text{EC}_{50}^\gamma)$

Model evaluation will include residual variability error term but will not include any random effects or covariate evaluation on fixed effect.

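### SAP 7.3 drops the protocol's ANCOVA and 90% confidence intervals for neopterin and MxA without a reason that covers them, and still asks for a CV of placebo baseline-adjusted AUEC

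*SAP*

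**What the plan says.** **Protocol.** Section 5.9.6.1, repeated in the synopsis, covers AUEC and maximum change for neopterin and MxA: "measures will be log-transformed and utilize an ANCOVA approach for calculating geometric means and 90% confidence intervals for each treatment". No covariate is named. Baseline is the natural reading, but it is an inference. Section 4.1 makes the values and variability of the neopterin metrics the primary endpoint.

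**SAP.** Section 7.3.1 takes baseline-adjusted AUEC and maximum increase as the primary neopterin metrics. For both drugs and placebo they are listed and "summarized using descriptive statistics (n, mean, SD, coefficient of variation, minimum, median, interquartile range, and maximum) for each treatment arm". Section 7.3.2 repeats this for MxA. Neither section contains a model, a covariate or an interval.

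**Reason given.** The Change Log explains the move from geometric mean to mean: "Changes in PD parameter from baseline for placebo and low doses may have negative values". It says nothing about ANCOVA or confidence intervals.

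**Baseline.** SAP 6.1 already defines the value an ANCOVA would need: "samples from Day 1, time 0 will be used for calculating this derived metric", with check-in and then screening as fallbacks.

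**The concern.** The study exists to inform the design of later similarity studies, so its main product is a set of means and SDs together with how well they are known. The protocol promised an adjusted estimate and a 90% interval for each treatment. The SAP prints neither, and its one explanation addresses a different matter, the log scale.

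The adjustment could also matter for precision. The baseline-adjusted metric normally subtracts a single pre-dose sample, so variation in that sample carries into every subject's result.

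Finally, the SAP gives up the geometric mean because placebo changes can be negative, yet keeps the CV for the same arm and metric. A CV divides by a mean that should be near zero there.

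**Working it through.** **1. The plan's own figures.** 7 arms × 12 = 84, and 84 + 14 replacements = 98; both reproduce. Neither document gives a mean, SD, CV or baseline correlation for neopterin or MxA, so everything below is per unit SD or rests on a stated assumption.

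**2. What the stated reason covers.** A log or geometric mean needs positive values. Negative changes therefore rule out log-scale analysis of baseline-adjusted metrics, including the change-from-baseline AUEC in protocol 5.7.2.3.1. A mean, a t-interval and an ANCOVA on the untransformed scale do not need positive values. The reason covers the log scale and nothing more.

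**3. Whether SAP 7.5 fills the gap.** Its response measures are neopterin only: "The dose- and exposure-response relationship between baseline-adjusted AUEC for neopterin and" the maximum neopterin change. It pools arms: "Data for all dose levels for a drug, as well as placebo, will be combined for the analysis". It excludes covariates: "Model evaluation will include residual variability error term but will not include any random effects or covariate evaluation on fixed effect". Parameter confidence intervals are used to choose among models, but there is no per-arm interval and nothing for MxA.

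**4. Width of the missing interval.** Half-width of the per-arm 90% interval for a mean at n = 12: t(0.95, 11)/√12 = 1.796/3.464 = 0.52 SD. With one SD pooled over four arms and one covariate (43 df): 1.681/3.464 = 0.49 SD.

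**5. CV of placebo baseline-adjusted AUEC.** Assume normal values, n = 12 and true mean 0. Then |CV| = SD/|mean| = √12/|t|, with t on 11 df.
- 5th percentile: 3.464/2.201 = 1.57, or 157% (158% in one simulation).
- 95th percentile: 3.464/0.0642 = 54.0, or about 5,400%.
- The sign follows the sample mean, so it is negative in 50% of samples.

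For other true means, P(negative) = Φ(−√12 × mean/SD). Simulated 5-95% ranges (of positive values at ratio 0.5):

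| True mean/SD | True CV | Negative | 5-95% range of CV |
|---|---|---|---|
| 0.5 | 200% | 4% | 87% to 871% |
| 1 | 100% | under 0.1% | 55% to 198% |
| 2 | 50% | 0% | 31% to 74% |

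The fault lies where the expected change is near zero. Maximum increase is much less affected. With no drug effect and independent, equal-variance samples (an assumption), its mean/SD is 1.45 with 13 post-dose samples and 1.58 with 17. Its CV then runs 41-110% and 38-98%.

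**6. What the covariate could gain.** With equal SDs and HC3 robust standard errors, the half-width is 0.51 SD if the correlation between baseline and metric is 0. At an assumed 0.5 it is 0.51 × √(1 − 0.5²) = 0.44 SD.

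**7. Why a single pooled SD is unsafe.** In simulated trials of four arms of 12 with one baseline covariate, I assumed SD ratios from placebo to high dose of 0.25/0.5/0.75/1 and 0.5/0.67/0.83/1. Nominal 90% coverage in the high-dose arm was 74-75% and 80% with a pooled SD. It was about 90% with HC3 and 90% with per-arm t-intervals.

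**The case against.** **This is a pilot and the SAP already reports what it needs.** There is no formal sample-size calculation and no hypothesis test, and mean, SD, median, interquartile range and range are all printed. A per-arm t-interval follows from n, mean and SD. SAP 7 puts all data in listings, so anyone with the listings can fit an ANCOVA. This stands, and it limits the impact. It does not explain why the precision of a primary endpoint, promised in the protocol, should be left to the reader.

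**The SAP's summaries may be safer than the protocol's model.** Step 7 supports this in part: a pooled-SD ANCOVA can under-cover the high-dose arm. That argues for arm-specific or robust variances, not for leaving out the intervals.

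**Nobody would plan from a placebo CV.** Probably true, and the other placebo statistics remain valid. But a required table entry that can be negative or in the thousands of percent informs no one.

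**Stronger readings the documents do not support.** A reader might infer that the ANCOVA was removed in SAP version 2 without being recorded. Version 1 was not supplied, so when and why it was dropped is unknown. A reader might infer that the SAP breaks an explicit commitment to a baseline covariate, but the protocol never names one. A reader might conclude that CVs in the active arms are unusable; without any mean or SD in the documents, that cannot be said. Restoring the protocol's log-scale analysis unchanged is not the answer either, because the negative-value objection to it is sound.

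**Conclusion.** The concern holds. The current SAP departs from protocol 5.9.6.1 for both biomarkers and both metrics. Its reason justifies abandoning logs and geometric means, but not the ANCOVA adjustment or the 90% intervals, and SAP 7.5 is no substitute. The CV for placebo baseline-adjusted AUEC is uninterpretable if the true placebo change is near zero, which is the ordinary expectation and fits the SAP's own remark about negative values.

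The impact is moderate to minor. No estimate already planned becomes wrong, no test is affected, and the missing results can be rebuilt. The size of the CV problem rests on normal data and a true mean of zero. The gain from the covariate rests on an unknown correlation and may be nil.

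**What to change.** In SAP 7.3.1 and 7.3.2:

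1. **Intervals.** Print per-arm 90% t-intervals for the mean of baseline-adjusted AUEC and maximum increase. If an interval for the SD is added, state that it assumes normality, or use a bootstrap. With lognormal data (an assumption), the nominal 90% chi-square interval covers 83%, 74% and 59% at CVs of 30%, 50% and 80%.
2. **Adjustment.** Add an untransformed ANCOVA with the Day 1 time-0 baseline as covariate. Fit it per drug with placebo over the same sampling window; for Avonex, cut placebo at Day 7, because SAP Attachment A samples arm G to Day 14. Use arm-specific variances or robust standard errors, and report adjusted means with 90% intervals.
3. **CV.** Omit it for placebo baseline-adjusted AUEC. In active arms print it beside the mean, its 90% interval and the SD. Do not mark values as unfit for planning when the interval reaches zero. Only arms with a sample CV below 1/0.518 = 193% would escape the mark, so at a true CV of 200% every unmarked value would be too low (median about 134%).
4. **Reason.** State why the SAP leaves the protocol's log-scale ANCOVA.

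A log-scale analysis of unadjusted AUEC is optional and supportive only. It is feasible because non-PK values below the limit "will be considered equal to the lower limit of quantification for all analyses unless explicitly noted otherwise", so the area stays positive. But untreated baseline dilutes differences: if the drug effect is 30%, 50% or 70% of total AUEC (assumed), a 30% smaller effect gives a ratio of 1 − 0.3 × share = 0.91, 0.85 or 0.79.

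**Cost.** SAP wording and a little more analysis on data already collected. Per-arm intervals are slightly wider than pooled ones when SDs are equal (0.52 against 0.49 SD).

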#### **7.3.2 MxA**

Individual MxA versus time plots will be presented for each participant. For MxA, baseline-adjusted AUEC and maximum increase from baseline will be calculated for each participant using all on treatment timepoints. Calculations will be performed using non-compartmental analysis packages available in a statistical software. The secondary analysis with MxA will use baseline-adjusted AUEC and maximum increase from baseline. Other derived measures (AUEC, pAUEC) for MxA may be calculated to evaluate how derived PD metrics impact trial design. PD parameters of IFN  $\beta$ -1a and pegIFN  $\beta$ -1a, and placebo groups will be listed and summarized using descriptive statistics (n, mean, SD, coefficient of variation, minimum, median, interquartile range, and maximum) for each treatment arm.

### **7.4. Pharmacokinetic Analysis – IFN $\beta$ -1a and pegIFN $\beta$ -1a**

Individual serum concentration versus time plots for IFN  $\beta$ -1a and pegIFN  $\beta$ -1a will be presented for each participant.  $AUC_{0-\text{inf}}$  and  $C_{\text{max}}$  will be calculated for each participant using all on treatment timepoints as part of the secondary analysis. In addition, the following PK parameters will be calculated for each individual as exploratory analyses:  $AUC_{0-t}$ ,  $T_{\text{max}}$ , apparent clearance (CL/F), apparent volume of distribution (V/F), elimination rate (Kel), and terminal half-life ( $t_{1/2}$ ). PK

parameters will be calculated for each participant using all on treatment timepoints. All parameters will be summarized using descriptive statistics (n, geometric mean, coefficient of variation, minimum, median, interquartile range, and maximum) for each IFN  $\beta$ -1a and pegIFN  $\beta$ -1a treatment arm.

Calculations will be performed using non-compartmental analysis packages available in a statistical software. Serum concentrations below the limits of quantification will be set to zero for the purpose of this analysis. Subjects with all samples below the limit of quantification will be excluded from PK summaries.  $AUC_{0-\text{inf}}$ ,  $t_{1/2}$ , and  $K_{el}$  for subjects will only be included for subjects with 3 or more concentration values on the terminal portion of the pharmacokinetic curve and with an adjusted coefficient of determinations ( $R^2$ ) greater than 0.80.

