### **4.2. Secondary Endpoints**

The secondary endpoints of this study are:

1. The values and variability of standard PD metrics (AUEC and maximal difference at a single time-point) for MxA at low, intermediate, and high doses of interferon beta-1a and peginterferon beta-1a.
2. The values and variability of pharmacokinetic characteristics ( $C_{max}$  and AUC of free drug concentration) at low, intermediate, and high doses of interferon beta-1a and peginterferon beta-1a.
3. Parameters ( $E_{max}$ , and  $EC_{50}$ ) calculated by the model after combining data from low, intermediate, and high doses of interferon beta-1a and peginterferon beta-1a with placebo data.

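### Leaving dosed subjects with no quantifiable sample out of the PK summaries raises an arm's Cmax geometric mean and median and almost always lowers its CV; their zero exposure in the Emax fit needs a companion fit without them

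*SAP*

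**What the plan says.** **Summaries.** SAP 7.4: "Subjects with all samples below the limit of quantification will be excluded from PK summaries". SAP 5: "Subjects with all samples below the lower limit of quantification will not be included in PK population summaries". The statistics affected are n, geometric mean, CV, minimum, median, interquartile range and maximum for each active arm. Cmax is a secondary endpoint in SAP 4.2. Protocol 4.2 names as an endpoint "The values and variability of pharmacokinetic characteristics" (Cmax and AUC) at each dose level.

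**Exposure-response.** SAP 5 defines the PK/PD population to include placebo, "as well as subjects with PK samples below the lower limit of quantification". SAP 6.1: "Pharmacokinetic measurements below the quantification limits will be considered equal to zero for all analyses". SAP 7.5 uses AUC0-inf as the exposure measure and says: "Data for all dose levels for a drug, as well as placebo, will be combined for the analysis". It lists linear, Emax and sigmoidal structures: "Model selection will be based on the initial graphical assessment and will be selected from one of the following structures".

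**Terminal-phase rule.** SAP 7.4 says that AUC0-inf, half-life and Kel "will only be included for subjects with 3 or more concentration values on the terminal portion of the pharmacokinetic curve", with adjusted R² above 0.80.

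**The concern.** The excluded subjects were dosed and gave samples. Their Cmax is known to lie below the limit, while every retained subject's Cmax lies at or above it. The exclusion therefore always cuts the arm from below and cannot average out.

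The primary objective in SAP 2.1 is to supply operating characteristics for later similarity studies, so the level and spread of Cmax by dose are part of what the study delivers. An affected dose would look higher and less variable than it was in the subjects dosed. The low doses are a quarter of the high doses, and SAP 3.2 says that doses were chosen for the range of neopterin. Nothing is said about assay sensitivity.

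AUC0-t, an exploratory parameter, would move in the same direction. AUC0-inf summaries are not changed by the exclusion sentence, because the terminal-phase rule already removes these subjects. Neopterin and MxA summaries and the dose-response ED50 are untouched.

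In the exposure fit the issue differs: dosed subjects with a small but positive exposure would be entered as exact zeros beside placebo.

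**Working it through.** **Inputs.** From SAP 3.2: 12 per arm (7 × 12 = 84, plus 14 replacements = 98, as stated). The documents give no quantification limit, BLQ rate or Cmax CV, so there is no plan figure to reproduce on this point. Assumed: lognormal Cmax with CV 50%, and the k lowest of 12 being the all-BLQ subjects.

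**Step 1, log-scale SD and sampling error.** σ = √ln(1 + 0.5²) = √0.2231 = 0.472. The 90% sampling range of a geometric mean with n = 12 is exp(±1.645 × 0.472/√12) = exp(±0.224), or -20% to +25%.

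**Step 2, Cmax with the k lowest removed.** The geometric mean and CV rows are medians over 200,000 simulated arms of 12, each compared with the same arm in full. The arm-median row is the large-sample value exp(σ·z) - 1, where z is the normal quantile at 0.5 + k/24 (0.105, 0.210, 0.319, 0.431).

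| | k = 0 | k = 1 | k = 2 | k = 3 | k = 4 |
|---|---|---|---|---|---|
| Geometric mean | – | +7.0% | +13.6% | +20.1% | +26.8% |
| Geometric CV | 48% | 42% | 38% | 35% | 32% |
| Arm median | – | +5% | +10% | +16% | +23% |

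The geometric mean rose in every arm. The geometric CV fell in 99.2% to 99.5% of arms. The SAP does not say which CV it means; the arithmetic CV fell at least as often. A fall is not certain: eleven values of 0.95 or 1 and one of 8 give a geometric CV of 0.66, and dropping the lowest (0.95) gives 0.69.

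Other assumed CVs, k = 1 to 4: the geometric mean rises by 4, 8, 12 and 16% at CV 30%, and by 11, 21, 31 and 42% at CV 80%.

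**Step 3, against the true value.** With one subject removed, the CV is below the true 50% in 76% of arms, against 56% with none removed. The geometric mean is above truth in about 70%.

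**Step 4, consequence for sizing.** Sample size for a log-scale comparison is proportional to log variance. ln(1 + 0.42²)/ln(1 + 0.48²) = 0.1625/0.2073 = 0.78, so a study sized from an arm with one exclusion would be about 22% smaller than one sized from the full arm.

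**Step 5, how likely.** The chance of at least one all-BLQ subject among 12 is 1 - (1 - p)¹². At assumed rates p of 1, 5 and 10% it is 11, 46 and 72%.

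**Step 6, exposure fit.** Assumed: 12 placebo and 12 at each of relative doses 1, 2 and 4; Emax 100; five combinations of exposure CV (30 to 80%), EC50 (1 to 4 times the low-dose geometric mean AUC) and residual SD (15 to 25). The k lowest low-dose subjects are set to AUC zero. Shifts are paired medians against the fit with true AUCs.

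| | k = 1 | k = 4 |
|---|---|---|
| Emax-model EC50, at zero | about +2% to +7% | +16% to +29% |
| Emax-model E0, at zero | +0.7 to +2.4 | +2.9 to +9.6 |
| Emax-model EC50, excluded | within about 1% | within about 1% |
| Sigmoidal EC50, at zero | 0 to +3% | 0 to +3%; +16% where EC50 equals the low-dose geometric mean AUC |

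For scale, the sampling SD of E0 is 4 to 7, and the full-data EC50 has a 5th-95th percentile range of about -40% to +67% at best. A linear model has no EC50; AIC chose it in 30 to 37% of runs in the flattest setting.

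**The case against.** **Materiality is unknown.** Providing for all-BLQ subjects is routine drafting and no evidence that any will occur in an active arm; Attachment A also schedules PK draws for placebo, where such profiles are expected. Three or four of 12 has no basis in the documents. This stands, and every figure above is conditional.

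**The plan already discloses the exclusions.** SAP 7.4 reports n and individual plots, and SAP 7 lists excluded subjects. A reader could count them, but that does not correct the geometric mean or CV.

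**Exclusion follows from setting BLQ to zero,** since one zero makes a geometric mean zero or undefined. That is true, and restoring zeros is no remedy. Ranks avoid the difficulty.

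**A reader might infer that the CV is too low in 99% of arms.** That figure compares the retained subjects with the same arm in full. Against the true CV the contrast is 76% with 56%.

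**A reader might also infer that the SAP contradicts itself on exposure in 7.5,** because an all-BLQ subject cannot meet the terminal-phase rule and so has no AUC0-inf. The documents do not support this. SAP 5 keeps these subjects in the PK/PD population, and 6.1 supplies the zero. Applied to 7.5, the terminal-phase rule would also remove placebo, which 7.5 requires. It is best read as limited to PK summaries, although the SAP does not say so.

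**Conclusion.** The point holds and is worth considering. In any active arm with all-BLQ subjects, the Cmax geometric mean and median are higher, and the CV almost always lower, than in the full dosed arm. At an assumed CV of 50%, one exclusion moves the geometric mean by about 7% and the typical CV from 48% to 42%, which is small beside sampling error. Three or four exclusions (+20% to +27%) are comparable with it. Unlike sampling error, the shift in the geometric mean runs in one direction only.

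For SAP 7.5 the natural reading is AUC zero for these subjects. That coding biases an Emax-model EC50 and E0 upward under the assumed settings, slightly for one subject and materially for four; leaving the subjects out barely moves EC50.

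If no subject is all BLQ, nothing changes.

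**What to change.** **SAP 7.4.** Report the number of all-BLQ subjects in each active arm. Beside the geometric mean and CV, give the Cmax median and quartiles with these subjects counted as the lowest ranks, shown as below the limit where a quantile falls among them. With 12 subjects this returns the full-arm median exactly for up to five all-BLQ subjects, and the lower quartile for up to two.

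**SAP 7.5.** Add one sentence confirming that the terminal-phase rule applies to PK summaries only, and that dosed all-BLQ subjects enter the exposure fit at AUC zero. Show that fit a second time with them excluded.

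**Cost.** SAP wording and modest programming, with no new samples. If such subjects occur, the second fit adds at most four exposure analyses (two drugs × two neopterin measures).
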